Between group differences in study endpoint mean of each of the secondary outcomes: change in ambulation (6MWT, MSWS-12, Hauser Ambulation Index), change in cognition (eight subtests of the five BRB-N tests), and change in MSFC z-scores will be tested using multiple linear regression models adjusted for baseline score and other covariates. Mixed model analysis of repeated measures, utilizing data collected at all time points, will be used to test for between group differences in change over time in mean secondary outcome measures adjusted for covariates. Between group differences in the odds of EDSS progression will be tested using multiple logistic regression models adjusted for other covariates. Generalized estimating equation (GEE) models will be used to test for between group differences in change over time in progression rates adjusted for other covariates. Cox proportional hazards models (conditional on model assumptions being met) or Kaplan-Meier analysis will be used to test for between group differences in time to EDSS progression.

OCT Temporal Quadrant RNFL

OCT temporal quadrant RNFL measurements from one eye per subject will be used for analysis purposes; randomly selected unless the patient has a history of optic neuritis in which case the unaffected eye will be selected. Between group differences in change in OCT temporal quadrant RNFL thickness will be tested using a multiple linear regression model adjusted for baseline thickness and other covariates. Multiple linear regression models will also be used to test for between group differences in three year rate of change adjusted for other covariates. Separate mixed model analyses of repeated

measures will be used to test for between group differences in 1) change over time in RNFL thickness and 2) change over the 3 years in annualized rates of RNFL change.

Exploratory endpoints

Fatigue

Between group differences in study endpoint mean FSS will be tested using a multiple linear regression model adjusted for baseline FSS score and other covariates. Mixed model analysis of repeated measures, utilizing data collected at all time points, will be used to test for between group differences in change over time in mean FSS adjusted for covariates.

Other vision measures

Multiple linear regression models will be used to test for between group differences in LCVA scores adjusted for other covariates. Binocular LCVA scores will be used to test for a treatment effect on vision changes; monocular LCVA scores will be used for correlation with OCT measures (from the matching eye). Generalized estimating equation (GEE) models will be used to test for between group differences in change over time in vision loss rates adjusted for other covariates. In addition correlation of LCVA with OCT measures (RNFL and macular volume) will be evaluated using Pearson correlation analysis (Spearman correlation will be used if measures have skewed distributions).

Between group differences in mean OCT macular volume scan measures will be tested using multiple linear regression models adjusted for covariates. mixed model analyses of repeated measures will be used to test for between group differences in change over time in OCT macular volume measures.

7. Study Procedures

A. Schedule of study procedures:

1. Symptoms questionnaire for subjective adverse events at baseline, 3, 6 and 12 months and then annually.
2. Comprehensive metabolic panel (CMP) and hemoglobin A1C (HbgA1C) at screening, 6 and 12 months, and then annually.
3. EDSS and DEXA scan (both hips/femurs and lumbar spine) at screening and then annually.
4. OCT at baseline and then annually.
5. MSFC, T25FW, 6MWT, LCVA, MSWS-12, AI, FSS and BRB-N at baseline and then annually.
6. Practice sessions (at screening visit:
 - a. BRB-N - 1 practice session

- b. PASAT - 2 practice sessions (in addition to the one administered during BRB-N)
- c. 9HP - 3 practice sessions

Table 1. Study Schedule

	V1 Screen 0 to -4 wks	V2 Baseline M0	V3 *** M3	V4 M6	V5 M12	V6 M18	V7 M24	V8 M30	V9 M36
Informed Consent	X								
Inclusion/Exclusion	X								
Injection Training		X							
Blood Pressure		X	X	X	X	X	X	X	X
Weight		X	X	X	X	X	X	X	X
Safety Lab Tests^a	X			X	X		X		X
Skin & Edema Assessment		X	X	X	X	X	X	X	X
OCT		X			X		X		X
LCVA		X			X		X		X
EDSS	X				X		X		X
Timed 25-Ft Walk		X			X		X		X
9-Hole Peg Test	XXX	X			X		X		X
PASAT (apart from BRB-N)	XX								
6 Minute Walk Test		X			X		X		X
MS Walking Scale - 12		X			X		X		X
Fatigue Severity Scale (FSS)		X			X		X		X
Hauser Ambulation Index		X			X		X		X
Brief Repeatable Battery	X	X			X		X		X
DEXA Scan^b	X ^c				X		X		X
Randomization		X							
Symptom Questionnaire		X	X	X	X	X	X	X	X
Concomitant Medications		X	X	X	X	X	X	X	X
Unsolicited Adverse Events			X	X	X	X	X	X	X
Dispense Study Drug		X	X	X	X	X	X	X	
Return Drug Vials and Logs			X	X	X	X	X	X	X

^a Safety lab tests: comprehensive metabolic panel and hemoglobin A1C.

^b Bilateral hips and lumbar spine

^c DEXA scan may be omitted at the Screening Visit if subject provides results of DEXA scan done within the 3 months prior to the Screening Visit

*** The month 3 visit is primarily a safety visit to assess AEs and to assess any difficulties subjects may be having with study drug injections. No laboratory tests are done, and no physical exam other than the skin and edema assessment (which would be unlikely to yield abnormal findings at 3 months, since chronic steroid side effects would likely take longer to occur in the 3 day per month pulsed dosing). For patients traveling a long distance to the study, this visit might be much more conveniently done by phone.

While the preference is for the month 3 visit to be done on-site, it can (optionally) be done as a phone visit, e.g. for subjects who 1) are inconvenienced by coming in person for this visit, and 2) have prior experience with taking subcutaneous injections. If this option is chosen, then 1) 6 months' worth of study drug (rather than 3) must be given out at the baseline visit, 2) no study drug dispensing or drug return will occur at the month 3 visit, and 3) no skin and edema assessment will be done at the month 3 visit.

B. Treatment Administration:

ACTH (Acthar gel) and placebo will be provided by the funding sponsor and distributed to individual sites. The study medication will be self-administered at a dose of 80 units subcutaneously for 3 consecutive days every month for the duration of the study. The dose will be reduced to 40 units if the full dose cannot be tolerated. Specific training in the injection procedure will be done prior to the initial injection.

C. Study Staff

Each study site will have a local principal investigator (Fargo, [name]; Minneapolis, [name]; Milwaukee, [name]; other sites may be added in the future) who will oversee study operation at that site and be responsible for the acquisition and handling of study data according to the procedures outlined in this protocol. Each site will utilize a study neurologist or neurology nurse practitioner certified in EDSS administration, who will perform the EDSS, review safety and tolerability data and report AEs and SAEs. There will not be a separate "treating" and "examining" neurologist at each site. A backup study neurologist may be designated, in case the primary study neurologist is unavailable for a scheduled visit. Other study staff such as research coordinators or nurses may be assigned to assist in recruitment, scheduling, and study procedures. Study coordinators/nurses may administer all study assessments except the EDSS and the physical examination (e.g., MSFC, BRB-N, 6MWT, MSWS-12, AI, LCVA, and subject-reported AE assessments), as long as they have been specifically and adequately trained on administering these assessments. Alternatively, the site study neurologist (or backup) may administer these assessments as well. OCT and DEXA scans will be performed by operators trained in administering those tests. A study monitor will be designated from the primary study site (University of Minnesota, Minneapolis) and will oversee data collection and management, as well as visit all study sites to review compliance with study procedures.

D. Relapses

Patients with certain forms of progressive MS (SPMS, PRMS) may experience acute disease relapses in addition to gradual neurologic decline. MS relapses entail new or worsened

neurologic symptoms that typically evolve over days, last for weeks, and gradually improve. They commonly manifest as focal deficits in sensory and/or motor function, visual disturbance, brainstem/cerebellar symptoms (such as vertigo, diplopia or ataxia), bladder or bowel symptoms, gait impairment, or fatigue. Acute cognitive or behavioral symptoms are less common, but may occur. Relapse symptoms may eventually resolve completely, partially, or not at all.

This study is not designed to assess the effect of ACTH on MS relapses, but the occurrence of relapses could affect the study in several ways. First, relapse symptoms could affect study measures of neurologic function/disability (T25FW, EDSS, etc. – any of the study metrics could be affected), either because the study visit occurred during the relapse or because the relapse resulted in incomplete recovery. Second, relapse symptoms (or signs) could be reported (or interpreted by study investigators) as AEs. Third, relapses are commonly treated with short courses of corticosteroids, and side effects from corticosteroid therapy could be mistaken for or confounded with AEs related to study medication. While relapses are expected to be quite rare in the study population, due to these potential impacts on study measures it is important to identify the occurrence and timing of relapses and corticosteroid treatment in study subjects. This will be done via the following procedures:

1. Subjects will be instructed to contact their treating neurologist (who may or may not be a study investigator) if they think they may be experiencing an MS relapse.
2. Subjects will also be asked to notify their study contact (site study coordinator or investigator) to inform them of the possible relapse, including the nature of symptoms, date of symptom onset, presence of any concomitant medical illness (e.g. upper respiratory tract infection, urinary tract infection, recent surgery or trauma), and any other special circumstances. The study coordinator will enter this information on the Potential Relapse case report form.
3. Evaluation of the potential relapse will be done by, and at the discretion of, the subject's treating neurologist.
4. The subject will be asked to provide copies of the treating neurologist's clinic notes and/or other medical records related to the possible relapse (e.g., MRI reports) to study staff.
5. The local principal investigator will review the medical records and judge whether or not the subject experienced a relapse. This will be recorded on the Potential Relapse case report form (as Relapse or Not Relapse).
6. Treatment of the relapse or suspected relapse (e.g., with corticosteroids) will be allowed, at the discretion of the treating neurologist. The dates, dose and formulation of treatment will be reported to the study coordinator and logged on the Potential Relapse case report form.

E. Unscheduled Study Visits

Subjects will be asked to contact their study site if they develop new symptoms that are concerning to them. The local study coordinator will record the reported symptoms on the Unsolicited AE Form, which will be reviewed by the local investigator. An unscheduled study visit will occur if the local investigator deems these AEs as potentially serious, possibly related to study medication, and/or requiring in-person assessment. If the reported symptoms are interpreted as mild and/or unrelated to study medication, the subject may be referred to their primary physician or advised to report back by phone with updates about symptom

evolution/resolution. Unscheduled visits will not be routinely performed for suspected MS relapse (see section 7D, Relapses), although they may occur in this situation if the reported symptoms are interpreted as a possible treatment-related AE. Assessments/procedures performed at an unscheduled visit will include all of the assessments done at Visit 3 (see Table 1) with the exception of study drug distribution; any further assessments and/or procedures (e.g. physical examination, other tests, referrals) will be done at the discretion of the local investigator.

F. Early Termination and Intent to Treat

Once subjects are randomized, regardless of if or the length of time they have been on blinded treatment, they will be included in the efficacy (intent to treat) analysis if efficacy data are available (that is, if they have completed at least one annual follow-up visit). Subjects who withdraw (e.g., due to side effects) prior to completing the Month 12 visit will be asked to return the study drug to the site, and to participate in annual phone calls (Months 12 and 24), and to return to the site for the final visit at Month 36. Subjects who withdraw after completing the Month 12 visit will be asked to return the study drug to the site, and to complete the remaining annual study visits (i.e., Month 24 and Month 36) even though they are not receiving drug. Subjects are of course allowed to decline further participation, in which case they would be considered lost-to-follow-up.

G. Data Safety Monitoring

A DSMB will be formed and will consist of one MS specialist, one neurologist familiar with the evaluation and treatment of MS but not otherwise associated with the study, and the study biostatistician. A DSMB chairperson will be chosen from one of the two neurologists on the DMSB.

Safety data will be reviewed by the DSMB at 6 and 12 months and then annually, starting from the time the first subject receives a dose of study medication and ending at participant study completion (i.e., no active participants on study drug and enrollment closed). Reports from all DSMB meetings will be forwarded to the Institutional Review Board (IRB). Any SAEs or unexpected AE's reported at other times will be reviewed by the head of the DSMB and reported to other members of the DSMB if considered significant enough to warrant interim review by the full committee. In the event of unanticipated SAEs that reflect new or increased risk to the subjects and are considered possibly related to the study medication or procedures (UPIRTSO) the funding sponsor and all study sites will be notified within 48 hours of the local investigator learning of the event. The local IRB will be notified within that IRB's policy timelines (e.g., the University of Minnesota IRB will be notified within 10 business days). A detailed analysis of all AEs will be conducted at the end of the first year of the study. The efficacy measures will also be analyzed annually throughout the study to see whether any signal of benefit is appearing. However, the study will be terminated only if there are unacceptable adverse events, not because of lack of any efficacy signals since it may take the entire 3 year duration of the study for any

beneficial effect to become manifest. Study termination due to safety concerns will be at the discretion of the DSMB; no pre-specified stopping rules will be used.

8. Cytokine sub-study

There are multiple mechanisms by which melanocortins such as adrenocorticotrophic hormone (ACTH) might alter the course of multiple sclerosis (MS) in a beneficial way (16, 54). One such mechanism is altering the balance between pro-inflammatory and anti-inflammatory cytokines via direct immunomodulating effects of melanocortins on immune system cells. A sub-study will be performed (at the University of Minnesota site only) to evaluate the change in plasma cytokine levels in subjects receiving ACTH compared to those receiving placebo, in order to better elucidate the possible mechanisms of ACTH in MS.

Subjects enrolling in the main study at the University of Minnesota site will be invited to participate in the plasma cytokine sub-study as well. Subjects who enroll in the sub-study will, at the annual study visits when they have blood drawn for safety blood tests, have additional blood tubes drawn for the cytokine analysis (2 EDTA tubes). Tubes will be mixed, centrifuged, and then plasma aliquoted and stored at -80° C. Leukocytes (buffy coat) will also be aliquoted and mixed with *RNAlater* (a reagent that stabilizes RNA for future possible analysis of gene expression) and stored at -80° C. Leukocytes or whole blood samples will also be stored for possible future DNA analysis. The potential future RNA and DNA analyses are not currently planned as part of the sub-study, and subjects may opt out of this aspect (i.e. choose not to have genetic material stored) in the consent form.

Cytokine levels will be assessed with multiplex cytokine assays on the Luminex system, and will be performed by the Cytokine Reference Laboratory at the University of Minnesota. Approximately 25-30 analytes (cytokines, chemokines, growth factors, etc) will be measured. The current list of analytes planned for the study include: Eotaxin, FGF-2, G-CSF, GM-CSF, IFNa2, IFNg, IL-1b, IL-1ra, IL-2, IL-4, IL-5, IL-6, IL-7, IL-8, IL-9, IL-10, IL-12(p70), IL-13, IL-15, IL-17, IP-10, MCP-1, MIP-1a,b, TNFa, VEGF, M-CSF, and MIG. Assays will be performed in batches of 40 samples (in duplicate) at a time; thus each "batch" would correspond to 10 subjects worth of samples (10 subjects x 4 samples/subjects = 40 samples). We anticipate the total number of subjects to be enrolled in the sub-study to be between 30 and 80. Differences between the active (ACTH) and placebo groups for plasma levels of each analyte will be assessed with multiple linear regression models adjusted for covariates (e.g. age, gender, MS phenotype) and/or mixed model analyses of repeated measures.

9. References

1. J. Frischer *et al.*, The relation between inflammation and neurodegeneration in multiple sclerosis brains. *Brain*. **132**, 1175-1189 (2009).
2. C. Stadelmann, C. Wegner, W. Bruck, Inflammation, demyelination, and degeneration - recent insights from MS pathology. *Biochim. Biophys. Acta*. **1812**, 275-282 (2011).
3. W. Bruck, C. Stadelmann, Inflammation and degeneration in multiple sclerosis. *Neurological Sciences*. **24 Suppl 5**, S265-S267 (2003).

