ACTH is FDA-approved for treatment of MS relapses, infantile spasms, and multiple non-neurologic disorders. ACTH has both corticotropic and neurotropic properties (14), and has the potential to benefit both the inflammatory and neurodegenerative aspects of MS, respectively. Because of its corticotropic properties, long term use may result in steroid-related adverse effects (AE's). Administration of steroids as a pulsed regimen has been generally found to be well tolerated with few of the usual AEs associated with chronic corticosteroid use (12), although reduction in bone mineral density has been reported (15). The multiple mechanisms of ACTH action may offer advantages over steroids alone for the treatment of MS. Any slowing of progression resulting from treatment of progressive forms of MS with ACTH could be due to its corticotropic effects, its neuroprotective effects, and/or corticosteroid-independent effects on the immune response (16). A recent preliminary report evaluating pulsed ACTH versus pulsed MP as an add-on to interferons for treatment of RRMS found a significant benefit of pulsed ACTH (compared to pulsed MP) in reducing relapses over one year (17).

3. Hypotheses

1. ACTH administered as a monthly pulse (consisting of three consecutive days of subcutaneous injection) will be safe and well-tolerated in progressive MS patients.
2. Pulsed ACTH treatment will slow the progression of sustained physical disability of ambulation, as measured walking speed (T25FW), walking endurance (6 minute walk test, 6MWT), the Hauser ambulation index (AI), and the MS walking scale (MSWS-12), all validated measures related to ambulation in MS patients.
3. Pulsed ACTH treatment will slow the progression of sustained cognitive disability as measured by the Brief Repeatable Battery of Neuropsychological Tests (BRB-N), a measure of cognitive impairment that has been specifically validated for MS.
4. Pulsed ACTH treatment will reduce the proportion of subjects who show a sustained progression of the EDSS over the course of the study. (EDSS is a validated measure of overall MS disability).
5. Pulsed ACTH will reduce the decline in retinal nerve fiber layer thickness as measured by optical coherence tomography (OCT).

4. Inclusion and Exclusion Criteria

1. Inclusion criteria:
 - a. Male or female patients with a confirmed diagnosis of MS by McDonald criteria (18).
 - b. Age \geq 18 years.

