- j. Treatment with dalfampridine or compounded 4-aminopyridine will be permitted as long as treatment has been ongoing and stable for at least 3 months prior to randomization. Starting or stopping dalfampridine during study participation is strongly discouraged.
- k. Stimulant medications for fatigue (such as methylphenidate, modafinil, armodafinil, amantadine or dextroamphetamine) will be permitted, but subjects will be asked to not take these medications on study visit days until all study procedures/assessments are completed.
- l. Women who are pregnant, planning to become pregnant over the course of the study, or breastfeeding.
- m. Concurrent participation in another study involving the use of blinded investigational drug.

3. Pre-screening considerations

- a. Pre-screening for osteoporosis and diabetes: Since the study budget does not contain funds to cover the cost of screen failures, it is recommended that subjects be pre-screened for osteoporosis and diabetes, e.g., with a DEXA scan and diabetes screening test (fasting blood glucose, glycosylated hemoglobin, or oral glucose tolerance test) within 2 years prior to the screening visit. Whether or not to order these pre-screening tests (or to omit them at the risk of an uncompensated visit in the case of screen failure) will be left to the discretion of the local PI.
- b. Dalfampridine: Since most patients with progressive MS with EDSS 2.0-6.0 have some walking impairment, it follows that most will be candidates for treatment with dalfampridine (or other aminopyridine preparation). While this is permitted within the study, starting or stopping dalfampridine (or other aminopyridine) during the course of the study should be avoided, as this may confound the ambulation outcome measures in the study. It is recommended that for all patients, consideration of whether or not they should be treated with dalfampridine be done prior to enrollment. For subjects interested in enrolling and who have not had a trial of dalfampridine (and are deemed an appropriate candidate for this medication), a trial of dalfampridine is recommended to see if they benefit from it. Once the determination is made whether or not to continue dalfampridine, they may enroll in the study once they have been stable on (or off) dalfampridine/aminopyridine for 3 months.

5. Outcome measures

A. Ambulation

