A key outcome measure of this phase II study is the safety and tolerability of pulsed ACTH compared to placebo. Little background information on adverse effects of pulsed ACTH in MS is available. A preliminary report of a one-year study (17) reported generally no increase in adverse effects in MS subjects receiving pulsed ACTH compared to pulsed MP, and fewer "psychiatric episodes" in the ACTH group. Potential AEs of concern are primarily those related to corticotropin effects, i.e. common steroid-related AEs such as increased risk of infection, weight gain, glucose intolerance, osteoporosis, hypertension, fluid retention, electrolyte derangements, and mood or behavioral changes.

Safety and tolerability of ACTH will be assessed in three ways: via volunteered responses from subjects regarding AEs, by elicited responses regarding specific symptoms, and by laboratory and physical exam measures. The advantage of volunteered (unsolicited) responses is that they allow unexpected AE's to be assessed and tend to highlight more serious or distressing AEs, while elicited responses have the advantage of more sensitive detection of specific AEs of interest (32). The volunteered responses will be obtained by an investigator or study coordinator at each follow-up visit, asking the

subject "Have you had any medical problems since your last visit?" Responses will be recorded on a log and severity will be rated according to the Common Terminology Criteria for Adverse Events (CTCAE) version 4.03. Subjects may also report AE's by phone, and these will be rated and logged in a similar manner. Study personnel will contact subjects monthly (by phone, email, etc.) around the time of their scheduled study drug injections, to remind them of the injections and to check for any new AE. If a phone-reported AE is deemed serious or possibly serious, an unscheduled visit will be arranged to allow the local investigator to assess the AE more fully (see section 7E, Unscheduled Study Visits). Elicited responses will be assessed through a questionnaire that will explore insomnia, irritability, dyspepsia, injection pain, edema, dysgeusia, fatigue, vision, skin changes, and changes in menstruation.

Physical exam and laboratory measures will include objective measurements of weight, blood pressure, skin changes, edema, myopathy, cataracts, glucose, electrolyte abnormalities, bone mineral density (DEXA) and hepatic toxicity.

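### Pregnancy is an exclusion, but no pregnancy test is scheduled, so a site following the plan may check it by self-report alone before giving study drug

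*Combined protocol and SAP*

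**What the plan says.** Eligibility (Section 4) is open to both sexes: "Male or female patients with a confirmed diagnosis of MS by McDonald criteria". The lower age limit is 18 and there is no upper limit. Exclusion l then bars "Women who are pregnant, planning to become pregnant over the course of the study, or breastfeeding". It gives no method of verification, and it is the only place where the supplied text mentions pregnancy.

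The laboratory schedule in Section 7.A reads "Comprehensive metabolic panel (CMP) and hemoglobin A1C (HbgA1C) at screening, 6 and 12 months, and then annually". Footnote a of Table 1 defines the laboratory row in full: "Safety lab tests: comprehensive metabolic panel and hemoglobin A1C". No other row of Table 1 is a pregnancy test.

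Table 1 marks the inclusion/exclusion check at V1 only, in a window of 0 to 4 weeks before baseline. Randomisation and the first dispensing are both at V2. Section 5.C allows the screening and baseline visits to be combined.

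Section 5.B includes changes in menstruation in the symptom questionnaire, which covers "insomnia, irritability, dyspepsia, injection pain, edema, dysgeusia, fatigue, vision, skin changes, and changes in menstruation". The plan therefore expects some participants to be menstruating.

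**The concern.** An exclusion protects participants only as well as it is checked. Exclusion l has three parts. Planning a pregnancy and breastfeeding can only be established by asking. Pregnancy is different: it can be present without the woman knowing, and a simple test detects it. The plan schedules no such test, either at the visit where eligibility is judged or at the visit where drug is first handed out.

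What is at stake is exposure to study drug, from V2 onward, of a pregnancy that the plan intends to exclude. Safety and tolerability are the main objective stated in Section 6.B, so the gap lies in the area that matters most to this trial.

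**Working it through.** The plan states no figure on this point, so there is none to reproduce. The check is a comparison of passages, followed by one illustration of scale.

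**1. How the plan verifies exclusions that can be tested**

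| Exclusion (Section 4) | Test or threshold named in the criterion | Scheduled at screening (7.A, Table 1) |
|---|---|---|
| b, diabetes | Yes: fasting glucose, HbA1c or glucose tolerance test | Yes: metabolic panel and HbA1c |
| c, osteoporosis | Yes: DEXA T-score by region | Yes: DEXA (may be omitted if one was done in the preceding 3 months) |
| h, natalizumab users positive for JC virus antibody | Yes: antibody status, retested every 6 months under standard of care | No |
| l, pregnancy | No | No |

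Pregnancy is the only one of these four with neither a named test nor a scheduled one.

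**2. Timing**

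- Eligibility check: V1, between 0 and 4 weeks before baseline.
- Randomisation and first dispensing: V2.
- Scheduled pregnancy tests at V1: 0. At V2: 0. From month 3 to month 36: 0.

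Two consequences follow. With no test, the V1 check may rest on history alone. And a test tied only to V1 would leave up to 4 weeks uncovered before drug is dispensed.

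**3. Could a pregnancy recorded as a menstrual change alter the safety comparison?**

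Section 6.E compares specific adverse event rates with Fisher's exact test. Section 6.B plans 50 subjects per arm. The documents give no rate for pregnancy or menstrual change, so the counts below are assumed.

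With k events in one arm and none in the other, and equal arms of 50, the two-sided p-value is 2 × C(50,k) / C(100,k), capped at 1.

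- k = 1: 2 × 50/100 = 1.00
- k = 2: 2 × 1,225/4,950 = 0.49
- k = 3: 2 × 19,600/161,700 = 0.24
- k = 5: 0.056
- k = 6: 0.027

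Against an assumed background of 5 events in each arm, two extra in one arm (7 versus 5) give p = 0.76. It takes six events against none to cross 0.05, so one or two misrecorded pregnancies would not change the comparison.

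**The case against.** The strongest reply is that absence from Table 1 does not show absence from practice. The inclusion/exclusion row at V1 means that pregnancy status has to be assessed; only the method is unstated. Table 1 is not a complete list of eligibility tests either, since JC virus antibody status is required for natalizumab users and does not appear there. Sites may test under local policy, and the consent pages are not part of the text reviewed. This stands as a limit on the claim: a reader might infer that sites do rely on self-report, or that the exclusion cannot be verified, and the documents show neither. They show that a site may rely on self-report while following the plan exactly. The JC virus comparison helps the defence only in part, because exclusion h names the test and its frequency and exclusion l names nothing.

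A reader might also infer from the menstruation item that a pregnancy would be logged as a drug side effect and would bias the comparison between arms. The documents do not support this. Section 5.B describes elicited items as a sensitive way to detect events of interest and attributes none of them to the drug. The questionnaire is also given at baseline, and in both blinded arms. Section 5.B adds an open question at each follow-up visit and monthly contact, and Section 7.E allows unscheduled visits with further tests at the investigator's discretion. The calculation above shows that one or two miscounts would not matter in any case.

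**Conclusion.** The point holds as a gap in eligibility verification and participant safety. As written, the schedule permits study drug to be dispensed with the pregnancy part of exclusion l checked by history alone, up to 4 weeks earlier. The size is 0 scheduled tests among 100 planned subjects, of whom an unstated number are women able to become pregnant. No expected number of exposed pregnancies can be derived from the documents.

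The conclusion rests on two assumptions: that Section 7.A, Table 1 and footnote a state all the laboratory work required for every subject, and that no requirement for a pregnancy test sits in the pages not supplied. If such a requirement exists elsewhere, the remedy reduces to citing it in the schedule. The point does not bear on the primary endpoint, the sample size or the validity of the adverse event comparisons.

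**What to change.** Add to Section 7.A and to Table 1 a pregnancy test for women able to become pregnant, and require a negative result on file before randomisation and dispensing at V2. Tie the requirement to V2, not to V1 alone, so that the interval of up to 4 weeks is covered. Where screening and baseline are combined, the result must be available the same day, before randomisation; a test run on the safety blood sample might not be back in time. Exclusion l can then refer to this row.

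The cost is one inexpensive test for a subset of about 100 subjects, one row in Table 1, and an occasional screen failure. Section 4 notes that the budget does not fund screen failures, so any such cost would fall on the site.

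Testing every reported menstrual change on an existing blood sample is not part of this request. Table 1 marks the questionnaire at months 3, 18 and 30, when no safety bloods are drawn, and the month 3 visit may be done by phone. How a pregnancy arising on study is handled is for the sponsor and investigators to specify.
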